## **6.2 Medical and Procedure History**

### **6.2.1 Medical history diseases**

The summary of medical history will be based on the medical history at the time of entry into the previous studies.

The number and percentage of subjects with a medical history condition, including both resolved and ongoing conditions at the time of entry into the previous study, will be summarized overall and by primary MedDRA system organ class (SOC) and preferred term (PT) for the Safety Analysis Set.

### **6.2.2 Procedure history and concomitant procedures**

Medical procedures are not coded and will only be provided in subject data listings.

## **6.3 History of Epilepsy**

All of the following are summarized using data collected at the time of entry into the previous studies or from the Baseline Period of the previous studies.

### **6.3.1 Etiology of epilepsy**

The number and percentage of subjects with each type of etiology as specified on the CRF (genetic, congenital, etc) from the previous studies will be summarized for the Efficacy Analysis Sets. A subject will be counted as having a particular etiology if that etiology was either confirmed or suspected based on the investigator's assessment.

### 6.3.2 Epileptic seizure profile

The number and percentage of subjects experiencing each seizure type at any time prior to study entry will be summarized for the Efficacy Analysis Sets. The following seizure types will be summarized: I, IA, IA1 through IA4, IB, IB1, IB2, IC, II, IIA through IIF, III, and IV. A subject with a history of a more specific seizure type will be counted in all higher levels of seizure types (eg, a subject with a history of IB1 seizures will be counted for seizure types I, IB, and IB1).

### 6.3.3 Classification of epileptic syndrome

The number and percentage of subjects with each epileptic syndrome will be summarized for the Efficacy Analysis Sets. This summary will include the number and percentage of subjects within the following categories: localization-related epilepsy; idiopathic, symptomatic, and cryptogenic localization-related epilepsy; generalized epilepsy; and idiopathic, symptomatic, and cryptogenic generalized epilepsy.

### 6.3.4 Focus localization

The number and percentage of subjects with each category of focus localization (frontal, temporal, parietal, occipital) will be summarized for the Efficacy Analysis Set. Subjects may be counted in more than 1 category of focus localization.

### 6.3.5 History of epileptic seizures

History of epileptic seizures, including the number and percentage of subjects with a history of status epilepticus and quantitative summaries of epilepsy duration, age at onset of first seizure, and percent of life with epilepsy, will be summarized for the Efficacy Analysis Set.

### 6.3.6 Seizure types experienced during baseline of the previous study

The number and percentage of subjects experiencing each seizure type during the Baseline Period will be summarized for the Efficacy Analysis Set based on the Baseline seizure diary data from the previous studies. The following seizure types will be summarized: I, IA, IB, IC, II, and IIA through IIF.

Subjects will be counted for all higher levels of seizure type categories corresponding to the seizure types or seizure sub-types reported on the CRF.

## 6.4 Medications

Medications recorded on the Concomitant Medications CRF and the Concomitant Medications (AEDs only) CRF will be classified as either AEDs or non-AEDs based on the preferred drug name search criteria, which are documented outside of the SAP.

- The medication is not an AED if it does not meet the search criteria based on preferred drug name, regardless of which CRF is used for reporting the medication. However, further review will be performed for medications that are recorded on the Concomitant Medications (AEDs only) CRF but are not included in the AEDs search criteria;
- For non-benzodiazepine medications, if the medication meets the search criteria for an AED based on preferred drug name, then the medication will be classified as an AED regardless of indication and regardless of which CRF the medication is recorded on;

- For benzodiazepines (identified using the search criteria), if the benzodiazepine is recorded on the Concomitant Medications (AEDs only) CRF, then the benzodiazepine will be classified as an AED;
- For benzodiazepines (identified using the search criteria), if the benzodiazepine is recorded on the Concomitant Medications CRFs, then the benzodiazepine will not be classified as an AED.

After medications are classified as AEDs or non-AEDs, the standard date imputation algorithms for start and stop date of the medication and first dose and last dose of BRV in the study will be applied. If an AED was taken at any time during dosing with BRV, then the AED is classified as a concomitant AED.

#### **6.4.1 Non-AEDs taken at study entry**

The number and percentage of subjects taking non-AED medications at study entry for the previous double-blind study will be summarized by WHO-DRL primary therapeutic group (Anatomic Therapeutic Class [ATC] level 1), therapeutic subgroup (ATC level 2), and preferred drug name for the Safety Analysis Set.

#### **6.4.2 Number of previous AEDs**

The number and percentage of subjects taking an AED prior to entry into the previous study will be summarized by WHO-DRL preferred drug name for the Efficacy Analysis Set based on the following categorization: 0-1 AEDs, 2-4 AEDs, and  $\geq 5$  AEDs.

#### **6.4.3 History of previous AED use**

The number and percentage of subjects who had taken at least 1 AED prior to entry into the previous study will be summarized overall and by WHO-DRL preferred drug name for the Efficacy Analysis Set.

#### **6.4.4 AEDs taken at study entry**

The number and percentage of subjects taking AEDs at study entry for the previous double-blind study will be summarized by WHO-DRL preferred drug name for the Efficacy Analysis Set.

#### **6.4.5 Concomitant AEDs**

A concomitant AED is an AED which was taken during administration of BRV, regardless of the start and stop date of the AED. The number and percentage of subjects taking concomitant AEDs will be summarized by WHO-DRL preferred drug name for the Efficacy Analysis Set.

## **7 MEASUREMENTS OF TREATMENT COMPLIANCE**

Study drug compliance will not be assessed due to the complexities associated with the calculation and interpretation of study drug compliance for this study. Study drug dosing will be provided in subject data listings.

## 8 EFFICACY ANALYSES

Unless otherwise noted, all efficacy outcomes will be summarized for the Efficacy Analysis Set. The derivations of 28-day adjusted seizure frequency are described in detail in Section 3.8.1.2.

All summaries of efficacy data are descriptive; no statistical testing will be performed.

### 8.1 Statistical Analysis of the Secondary Efficacy Variables

#### 8.1.1 Percentage of subjects on continuous BRV monotherapy

The cumulative proportion of subjects able to achieve BRV monotherapy for 3, 6, and 12 months during the Evaluation Period will be summarized. BRV monotherapy is defined as continuous treatment with BRV only (ie, no treatment with another AED). Use of rescue AED medications for a duration of no more than 2 consecutive days will not disqualify a subject from being defined as on continuous monotherapy provided the use of rescue AED medication does not exceed more than 1 time per week.

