10.2.1 Permitted Concomitant Treatments (Medications and Therapies)

Subjects entering the present study in BRV monotherapy may require re-conversion from BRV monotherapy treatment to adjunctive treatment with BRV and another AED. In this case, as well as for subjects entering the study in add-on, the Investigator may adapt the concomitant AED drug/dosage for safety or efficacy reasons.

In case of excellent efficacy and tolerability of BRV, withdrawal of concomitant AED(s) resulting in monotherapy with BRV may be re-attempted by the Investigator.

Benzodiazepines (BZD) are allowed. If taken more than once a week (for any indication) BZDs will be considered as a concomitant AED.

Use of phenobarbital and primidone is allowed.

Use of felbamate is permitted if continuous exposure is at least 18 months before Visit 1.

Use of VNS is also allowed.

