13.1.3.2 Evaluation of Efficacy

13.1.3.2.1 Efficacy Analyses

All efficacy analyses will be based on the Efficacy Population. All efficacy variables will be analyzed descriptively. The Baseline of an efficacy variable will be the Baseline from the previous study.

The secondary efficacy variables for the cumulative proportion of subjects remaining on BRV monotherapy from the start of the study through 3, 6, and 12 months will be estimated using Kaplan-Meier methods.

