#### 2.1.2 Secondary objectives

To evaluate the maintenance of efficacy over time of BRV.

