#### 2.2.2 Efficacy variables

##### 2.2.2.1 Secondary efficacy variables

- Percentage of subjects on continuous BRV monotherapy for at least 3 months, at least 6 months, and at least 12 months of the Evaluation Period

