## **2.5 Changes from the Analysis Planned in the Protocol**

Percentage of subjects remaining on continuous BRV monotherapy from the start of the study through 3, 6, and 12 months will not be done because it would be limited to subjects entering on monotherapy and it was expected that this rate would be low due to the parent studies being stopped prematurely. Instead of this analysis, the cumulative proportion of subjects able to achieve BRV monotherapy for 3, 6, and 12 months during the Evaluation Period will be summarized.

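### The monotherapy variable in SAP 8.1.1 counts subjects who ever achieved 3, 6 or 12 months on BRV alone, and no planned table shows who later lost it

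*SAP*

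**What the plan says.** The secondary objective (SAP 2.1.2, Protocol 7.2) reads "To evaluate the maintenance of efficacy over time of BRV". One variable carries the label secondary efficacy (SAP 2.2.2.1): "Percentage of subjects on continuous BRV monotherapy for at least 3 months, at least 6 months, and at least 12 months of the Evaluation Period".

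Protocol 13.1.3.2.1 planned Kaplan-Meier estimates of the "cumulative proportion of subjects remaining on BRV monotherapy from the start of the study through 3, 6, and 12 months". SAP 2.5 withdraws that analysis. Its reason is that the analysis would be confined to subjects who enter on monotherapy, and few were expected because the parent studies stopped early. The replacement is stated there: "Instead of this analysis, the cumulative proportion of subjects able to achieve BRV monotherapy for 3, 6, and 12 months during the Evaluation Period".

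SAP 8.1.1 repeats the replacement: "The cumulative proportion of subjects able to achieve BRV monotherapy for 3, 6, and 12 months during the Evaluation Period will be summarized". It defines monotherapy by drug use alone: BRV with no other AED, apart from a short rescue allowance (at most 2 consecutive days, at most once a week). It has no rule for what happens to a subject's status after a qualifying spell, and it does not say when that spell may begin.

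Loss of monotherapy is foreseen. Protocol 10.2.1 says: "Subjects entering the present study in BRV monotherapy may require re-conversion from BRV monotherapy treatment to adjunctive treatment". The same section and SAP 2.3 let the investigator try again to withdraw the other AEDs.

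**The concern.** The protocol analysis and its replacement answer different questions. In *remaining on*, loss of monotherapy is the event and the curve falls when it happens. In *able to achieve*, a subject's status can move only from failure to success. A subject who completes 3 months on BRV alone, then adds a second AED or stops BRV, is still counted.

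Two things follow. The reported percentage says nothing about what happens after the qualifying spell. It also depends on how long subjects were followed, since longer follow-up gives more chances to qualify and none to be removed. A reader who sees a percentage under the heading of continuous BRV monotherapy, beside an objective about maintenance, could take it as evidence that monotherapy was sustained.

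**Working it through.** The plan gives no expected monotherapy rate, loss rate or sample size calculation, so there is no figure to reproduce. The inputs below are assumptions, except N = 108 (SAP 2.4, enrolled; it stands in for the Efficacy Analysis Set, whose size is not given) and the 30-day month (SAP 3.2.5).

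**1. The rule.** A subject is a success at k months (k = 3, 6, 12) if the longest spell on BRV with no other AED is at least 30 × k days. Events after a qualifying spell do not enter.

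**2. Same result, opposite outcomes.** Assume 720 days of follow-up for everyone and monotherapy from day 1 in the achievers.
- A: all achievers stay on monotherapy to day 720.
- B: all achievers lose it after day 360.

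| Achievers (assumed) | SAP 8.1.1 at 3, 6 and 12 months, A and B alike | On monotherapy at month 24, A | On monotherapy at month 24, B |
|---|---|---|---|
| 11/108 | 10.2% | 10.2% | 0% |
| 32/108 | 29.6% | 29.6% | 0% |
| 54/108 | 50.0% | 50.0% | 0% |

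The equality at all three thresholds needs every loss to fall after month 12, so this is the extreme case.

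**3. What the three thresholds do show.** Let 32 subjects start on day 1 and lose monotherapy at a constant rate L per 360 days. The percentage reaching m months is 100 × (32/108) × (1 − L)^(m/12).

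| L | 3 months | 6 months | 12 months | Still on at month 24 |
|---|---|---|---|---|
| 10% | 28.9 | 28.1 | 26.7 | 24.0 |
| 30% | 27.1 | 24.8 | 20.7 | 14.5 |
| 50% | 24.9 | 21.0 | 14.8 | 7.4 |
| 70% | 21.9 | 16.2 | 8.9 | 2.7 |

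The fall from 3 to 12 months therefore tracks loss, but not only loss. Suppose 16 subjects start on day 1, 16 start on day 541 (720 − 541 + 1 = 180 days available), and nobody loses monotherapy. The row is 32/108, 32/108, 16/108 = 29.6, 29.6, 14.8%. The 12-month figure equals that of the 50% loss row, yet 29.6% rather than 7.4% are on monotherapy at month 24. Dropout before a threshold has the same effect as a late start.

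**4. Dependence on follow-up.** Assume 20% are on monotherapy at entry, conversion is c = 1% a month and loss is h = 5% a month.
- Share on monotherapy at month t: 1/6 + (0.20 − 1/6) × 0.94^t, which is 18.3% at month 12 and 17.4% at month 24.
- Share ever completing a 3-month run: let u be the share off and not yet counted, and r0, r1, r2 the uncounted shares with 0, 1 or 2 months completed. Entrants start in r0 = 0.20, with u = 0.80; converters are credited with their month of conversion. Each month u becomes (1 − c)u + h(r0 + r1 + r2), r1 becomes cu + (1 − h)r0, r2 becomes (1 − h)r1, r0 becomes 0, and (1 − h)r2 is newly counted. The total is about 24% with 12 months of follow-up and 32% with 24.
- With conversion halved (c = 0.5%), the ever figure goes from about 21% to 25% while the share on monotherapy falls from about 15% to 12%.

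**5. Other planned tables.**
- SAP 5.1: the Kaplan-Meier estimate times discontinuation of BRV, not addition of an AED.
- SAP 6.4.5: counts concomitant AEDs by drug name at any time on BRV, without timing.
- SAP 8.2.1 and 8.2.2: POS frequency and percent reduction pool time on monotherapy with time on adjunctive treatment.
- SAP 8.2.3: seizure freedom, without regard to AED use.

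None shows loss of monotherapy.

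**The case against.** The strongest reply is that maintenance of efficacy is already addressed with seizure data. POS frequency and percent reduction are tabulated by 3-month interval and repeated within exposure duration cohorts, which SAP 4.2 offers as a way to view long-term outcomes without the influence of earlier dropouts. Seizure freedom over 6, 12, 18 months and longer is in 8.2.3. The exploratory objectives do not concern seizures, so these summaries naturally serve the secondary objective. All of this stands. A reader might infer that 8.1.1 is the only variable assigned to that objective, but neither document maps variables to objectives; they only label them secondary or other.

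It is also true that the change is declared and reasoned in SAP 2.5, so it is not a hidden departure. The protocol's own monotherapy variable used no seizure data either, so the absence of a seizure criterion is not something the SAP introduced. The protocol analysis also ended at 12 months. Setting the 8.1.1 figures against monotherapy status at 36 or 60 months would therefore be no fair measure of what the change cost. Finally, nothing is tested, so no formal decision turns on this row.

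What the reply does not meet is narrower. The protocol analysis had loss of monotherapy as its event; the replacement does not, and no other table supplies it. The reason in 2.5 concerns who could be included. It does not require giving up the loss event, because the clock can start whenever monotherapy starts.

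**Conclusion.** The concern holds as a point about persistence of monotherapy. SAP 8.1.1 is an ever-achieved proportion, it can only rise with follow-up, and loss of monotherapy appears in no planned table. This rests on the plain meaning of cumulative and able to achieve; the SAP does not itself say ever, and it states no reversal rule.

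A reader might go further and infer that the figure carries no information on maintenance, or that the plan leaves the secondary objective unsupported. Neither follows. The fall across the three thresholds gives crude persistence information, confounded by late starts and dropout, and the seizure-based summaries address maintenance at the level of other variables.

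The size cannot be fixed from the documents. Under the assumptions above, one reported value (29.6%) fits anything from 0% to 29.6% on monotherapy at month 24, and the reported 3-month figure rises by about 4 to 8 percentage points between 12 and 24 months of follow-up while the share on monotherapy falls slightly. Because the study is descriptive, the harm is misreading rather than a wrong test result. It is worth correcting because the correction is cheap.

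**What to change.** In SAP 8.1.1:
- Label the proportion *ever achieved*.
- Beside each of the 3-, 6- and 12-month rows, give the number and percent who later lost monotherapy. Show addition of another AED beyond the rescue allowance separately from BRV discontinuation, since the second mixes tolerability and consent withdrawal with efficacy.
- Add a descriptive Kaplan-Meier estimate from the first day of BRV monotherapy in N01315, whenever it starts, to its loss. Censor study completers still on monotherapy at last dose. This removes the objection in 2.5 that the analysis is limited to subjects entering on monotherapy.

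In SAP 2.5, state that the ever-achieved proportion is not by itself evidence of maintenance, and name the 3-month-interval POS summaries as the seizure-based evidence for the secondary objective.

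Do not add POS reduction during the qualifying spell among achievers. Subjects with poor control may be given another AED and leave the spell, so that summary conditions on the outcome and would tend to look favourable.

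The cost is some SAP wording, a few table rows and one Kaplan-Meier table, from dosing and AED dates already collected. The estimate may rest on few of the 108 subjects, and the added figures may look less favourable than the proportion alone.

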### 8.2 Analyses of Other Efficacy Variables

#### 8.2.1 Partial onset seizure frequency

Twenty-eight day adjusted POS frequency will be summarized with quantitative descriptive statistics for all subjects for the Baseline Period, the On Treatment Period, and by 3-month time intervals over the On Treatment Period. The summary over the On Treatment Period will include all subjects in the Efficacy Analysis Set. Similar summaries will be provided for the full cohort interval and by 3-month time intervals for each exposure duration cohort.

#### 8.2.2 Percent reduction in POS frequency

Percent reduction in POS frequency from Baseline to the On Treatment Period will be calculated as follows, where On Treatment Period Frequency is the 28-day adjusted POS frequency during On Treatment Period and Baseline Period Frequency is the 28-day adjusted POS frequency during the Baseline Period of the previous study.

$$\% \text{ Reduction} = 100 \times \frac{\text{Baseline Period Frequency} - \text{On Treatment Period Frequency}}{\text{Baseline Period Frequency}}$$

A similar calculation applies to each 3-month time interval over the On Treatment Period and for the cohort interval for each exposure duration cohort.

Percent reduction from Baseline for POS frequency will be summarized with quantitative descriptive statistics for the On Treatment Period, and by 3-month time intervals over the On Treatment Period. The summary over the On Treatment Period will include all subjects in the Efficacy Analysis Set. Similar summaries will be provided for the full cohort interval and by 3-month time intervals for each exposure duration cohort. Percent reduction from Baseline for POS frequency will be summarized in the same manner by geographic region.

#### 8.2.3 Specified Month seizure freedom

The numbers and percentages of subjects who are seizure free for all seizure types for any continuous 6-month interval, 12-month interval, 18-month interval, and so forth will be summarized overall for the period of time that subjects are being treated with BRV and by

Exposure Duration Cohort. The overall summary will present the number and percentage of subjects who reported no seizures for the specified duration of seizure freedom and the seizure diary was completed for at least 90% of days within the seizure-free interval. Subjects whose duration of BRV treatment was less than the specified duration of seizure freedom will be considered failures for seizure-freedom. Summaries by exposure duration cohort will present the number and percentage of subjects who reported no seizures for the specified duration of seizure freedom at any time during the cohort interval (eg, through the end of Month 6 for the 6-month cohort) and the seizure diary was completed for at least 90% of days within the seizure-free interval. Percentages are relative to the number of subjects within each Exposure Duration Cohort.

A subject is seizure free for a 6-month interval if the subject did not report any seizures in the 6-month interval and the seizure diary was completed for at least 90% of days within the seizure-free interval. The percentage of days for which seizure diary was completed within a given 6-month interval will be calculated as follows based on a 30-day month:

$$\% \text{ of days diary was done} = 100 \times \left[ \frac{180 - \text{number of days diary was not done in the interval}}{180} \right]$$

A similar calculation applies for 12-month seizure freedom based on 360 days, 18-month seizure freedom based on 540 days, and so forth.

#### **8.2.4 QOLIE-31-P**

The scoring algorithm for QOLIE-31-P is described in Section 3.8.2 and Section 13.1.

QOLIE-31-P is assessed at the following time points: Month 2, Month 6, Month 12, Month 18, and Month 24. QOLIE-31-P is also assessed at EDVs for subjects who discontinue prior to the YEV at the end of the second year.

Observed values for QOLIE-31-P total score and subscale scores for Seizure Worry, Daily Activities/Social Function, Energy/Fatigue, Emotional Well-Being, Cognitive Function, Medication Effects, Overall Quality of Life, and Health Status will be summarized for Baseline and Last Value for the Efficacy Analysis Set. Additionally, observed values will be summarized for Baseline, EV, and by visit for each study visit cohort. For summaries of observed values at each time point, only subjects with a change from Baseline value at that time point will be summarized. Additionally, the mean and SD for each Baseline score will be provided at each post-Baseline time point for subjects included in the summary of change from Baseline.

Similar summaries will be provided for QOLIE-31-P distress items Seizure Worry, Daily Activities/Social Function, Energy/Fatigue, Emotional Well-Being, Cognitive Function, Medication Effects, and Overall Quality of Life.

The rankings of prioritization items (Seizure Worry, Daily Activities/Social Function, Energy/Fatigue, Emotional Well-Being, Cognitive Function, Medication Effects, and Overall Quality of Life) will be summarized by visit for the first 2 years of the Evaluation Period, and for Last Value for the first 2 years of the Evaluation Period for the Efficacy Analysis Set. Only observed values will be summarized and only the number of non missing values and the means for each item will be presented.

